4.3 STUDY TREATMENT

The investigational medicinal product (IMP) for this study is tenecteplase. This will be given to patients in combination with heparin, as outlined in section 3.3.1.

4.3.1 Study Treatment Formulation, Packaging, and Handling

4.3.1.1 Tenecteplase

Tenecteplase will be supplied by Genentech as a sterile, lyophilized powder in a 50-mg vial under partial vacuum. Sites will be expected to provide the diluent, 10mL Sterile Water for Injection.

Placebo will be supplied by Genentech as a sterile lyophilized powder in a 50 mg vial under partial volume that will be labeled as Tenecteplase Placebo 50mg.

For information on the formulation and handling of tenecteplase, see the local prescribing information for Tenecteplase or the Tenecteplase Investigator's Brochure.

4.3.2 Study Treatment Dosage, Administration, and Compliance

The treatment regimens are summarized in Section 3.3.1.

Any overdose or incorrect administration of tenecteplase or placebo should be noted in the patient's medical records and reported according to Section 5.5 (Special Situations Reports). Adverse events associated with an overdose or incorrect administration of any of the study treatments should be recorded in the patient's medical records.

4.3.2.1 Tenecteplase

Store lyophilized Tenecteplase at controlled room temperature not to exceed 30°C (86°F) or under refrigeration 2°C–8°C (36°F–46°F). Do not use beyond the expiration date stamped on the vial.

For information on the formulation and handling of tenecteplase, see the local prescribing information for Tenecteplase or the Tenecteplase Investigator's Brochure.

Please see section 3.3.1 for dosing schedule.

4.4 CONCOMITANT THERAPY

Concomitant therapy consists of any medication (e.g., prescription drugs, over-the-counter drugs, vaccines, herbal or homeopathic remedies, nutritional supplements) used by a patient in addition to protocol-mandated treatment from 7 days prior to initiation of study treatment to the treatment discontinuation visit. All such medications should be reported to the investigator and recorded in the patient's medical records. Medications indicated as "prn" or "as needed" will not be reported in the EDC.

4.4.1 Cautionary Therapy

Concomitant therapy includes any medication (e.g., prescription drugs, over-the-counter drugs, herbal/homeopathic remedies, preventative vaccines, vitamins, nutritional supplements) used by a patient from 1 week prior to randomization to the patient's last visit. All concomitant medications should be reported to the investigator and recorded on the Concomitant Medications eCRF.

Tenecteplase–Icahn School of Medicine at Mount Sinai
Protocol ML42492

16

Patients who use oral contraceptives or maintenance therapy for comorbidities should continue their use.

Formal interaction studies of tenecteplase with other drugs have not been performed. Patients studied in clinical trials of tenecteplase were routinely treated with heparin and aspirin. Anticoagulants (such as heparin and vitamin K antagonists) and drugs that alter platelet function (such as acetylsalicylic acid, dipyridamole, and glycoprotein [GP] IIb/IIIa inhibitors) may increase the risk of bleeding if administered prior to, during, or after tenecteplase therapy.

The investigator should consult the prescribing information when determining whether a concomitant medication can be safely administered with study treatment. In addition, the investigator should contact the Medical Monitor if questions arise regarding medications not mentioned above.

4.4.2 Prohibited Therapy

Use of the following concomitant therapies is prohibited as described below:

- Investigational therapy (other than protocol-mandated study treatment) is prohibited within 30 days prior to initiation of study treatment, during study treatment, and until the patient's last study assessment.

4.5 STUDY ASSESSMENTS AND PROCEDURES

The schedule of activities to be performed during the study is provided in Appendix 1. All activities must be performed and documented for each patient. Patients will be closely monitored for safety and tolerability throughout the study. Patients should be assessed for toxicity prior to each dose; dosing will occur only if the clinical assessment and local laboratory test values are acceptable.

4.5.1 Informed Consent

Written informed consent for participation in the study must be obtained before performing any study-related procedures (including screening evaluations). Informed Consent Forms for enrolled patients and for patients who are not subsequently enrolled will be maintained at the study site. Given the circumstances that may exist at sites due to COVID-19, sites will work with their IRBs to determine the best method of obtaining consent. This may be in person or electronically depending on requirements.

 - All women of childbearing potential will have a pregnancy test at screening. If a urine pregnancy test is positive, it must be confirmed by a serum pregnancy test.

- SARS-CoV-2 PCR Test**

A SARS-CoV-2 PCR Test will be conducted during screening to determine if the patient is COVID positive.

- Respiratory Status / Ventilator Settings**

Respiratory or Ventilator settings will be collected at Screening.

Tenecteplase–Icahn School of Medicine at Mount Sinai
Protocol ML42492

- Ventilator settings (if appropriate): RR, TV, PI (if PCV or PSV) FiO2, PEEP, Plateau Pressure
- NIPPV settings (if appropriate): RR, IPAP, EPAP, FiO2
- HFNC settings (if appropriate): FiO2, flow
- NRB settings (if appropriate): flow
- **Ordinal Scale Assessment**

The Ordinal Scale Assessment will be conducted daily to determine the patient's current status.

- **Imaging**

If the patient has a standard of care CT Scan or X-Ray performed, the imaging result will be captured in the Screening CRF.

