1.5 STUDY RATIONALE AND BENEFIT-RISK ASSESSMENT

Based on a recent JAMA publication, intubated COVID-19 patients in NYC can expect a mortality rate as high as 88%.¹⁶ This dismal mortality rate has driven us to make clinical decisions regarding the use of off-label application of otherwise FDA approved medications in a hope to improve outcomes. Therefore, we undertook the off-label utilization of tenecteplase (at the lower EXTEND-IA TNK dosing) with concomitant heparin administration for the treatment of 5 refractory COVID-19 patients. We were highly encouraged by this experience in that all patients had improvement in oxygenation, alveolar ventilation, and hemodynamics within 24-48 hours. Four of the five patients had shock resolution, while the fifth patient had dramatic reductions in vasopressor requirements. No clinically significant bleeding was noted in any of these patients. As a result, we believe that a high-quality prospective Phase II, dose escalation trial is indicated.

To assess the efficacy of tenecteplase on critically ill patients with COVID-19 and hypoxic respiratory failure, we propose a multi-center, randomized, controlled, double-blind, dose-escalation trial comparing tenecteplase versus placebo. We intend to enroll 60 subjects: 40 randomized for intervention (20 each at doses of TNK, 0.25 mg/kg and 0.50 mg/kg) and 20 for placebo. Planned inclusion criteria are confirmed respiratory failure requiring mechanical ventilation for not greater than 48 hours, or non-rebreather (NRB), high-flow nasal cannula (HFNC), or non-invasive positive pressure ventilation (NIPPV) for less than 96 hours, with confirmed infection with SARS-CoV-2 virus (PCR positive within 14 days), elevated D-dimer (2 times upper limit of normal,¹⁷ and lack of stringent exclusion criteria. Primary efficacy outcome will be clinical status assessment at 28 days (proportion of patients alive and free of respiratory failure). Primary safety outcome will be rate of ICH or major acute hemorrhage (defined as bleeding episode leading to hemodynamic compromise requiring emergency intervention [such as replacement of fluid and/or blood products, inotropic support, or surgical treatment], or life-threatening or fatal bleeding). Secondary outcomes include survival, ventilator-free days, respiratory failure-free days, vasopressor-free days, improvement in PaO₂/FiO₂, and ICU and hospital length of stay.

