2.3 STUDY OUTCOMES

The following outcomes will be tracked for the trial:

Primary outcome is: the proportion of patients alive and free of respiratory failure (not requiring non-rebreather, high-flow nasal cannula, non-invasive positive pressure ventilation, or mechanical ventilation) at 28 days

- A. Primary safety outcome: Occurrence of intracranial bleeding or major bleeding (Definition: A bleeding episode leading to hemodynamic compromise requiring emergency intervention (such as replacement of fluid and/or blood products, inotropic support, or surgical treatment), or life-threatening or fatal bleeding) within 72 hours of randomization. All outcomes will be assessed in a blinded fashion by the DSMC/CEC.
- B. Secondary outcomes include: 14-day in-hospital mortality, 28-day mortality, ventilator-free days, respiratory failure-free days (not requiring NRB, HFNC, NIPPV, or mechanical ventilation), vasopressor-free days, vasopressor requirements at 24 and 72 hours, P/F ratio at 24 hours and 72 hours, ICU-free days, hospital length of stay, new renal failure, need for renal replacement therapy
- C. Mortality: given a high mortality rate amongst this patient population, patients who die will be included in statistical analysis. Variables of interest will be calculated until the point these patients expire.

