4.1.1 Inclusion Criteria

Patients must meet the following criteria for study entry:

- Patient/legally authorized representative has completed the Informed Consent Form
- Age ≥ 18 years
- Ability to comply with the study protocol, in the investigator's judgment
- Respiratory failure secondary to COVID-19 requiring mechanical ventilation for no greater than 48 hours, or high-flow nasal cannula (HFNC), non-rebreather (NRB) mask or non-invasive positive pressure ventilation (NIPPV) for less than 96 hours
- Confirmed infection with SARS-CoV-2 virus (PCR positive within 14 days)
- Elevated D-dimer (>2 times upper limit of normal within past 72 hours)
- For patient who are intubated >12 hours prior to randomization or with any evidence of neurologic deficit a head CT within 12 hours demonstrating no evidence of acute or subacute infarct or hemorrhage

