Appendix 1: Study Flowchart

- a. Randomization will be done using an escalating-dose randomized design. It will be block randomization of 10:5 (treatment:control) performed twice per dose of TNK-tPA. If no safety triggers occur after 20 patients enrolled at the low dose, then the high dose enrollment will be undertaken with block randomization of 10:5.
- b. Vital signs include respiratory rate, pulse rate, systolic and diastolic blood pressure and temperature. Vitals are to be measured within 60 minutes prior to each tenecteplase infusion and, if clinically indicated, during or after the infusion.
- c. Labs to be collected include: CBC: Platelet, WBC, Hb, Hct; BMP: Na, K, Cl, HCO3, BUN, Cr; Glucose (finger stick or lab); LFT: ALT, AST, Bili, Alk Phos, LDH, Total Protein, Albumin, D-dimer, fibrinogen, CRP, ferritin, troponin-I; Coagulation: INR, aPTT, Anti-Xa, PT (only if the patient is taking an anticoagulant); Thromboelastograms
- d. Only coagulation labs need to be checked every 6 hours post randomization which includes: INR, aPTT, PT (only if the patient is taking an anticoagulant)
- e. Arterial blood gases to be collected include: Arterial Blood Gas: pH, pCO2, pO2, SaO2, Lactate
- f. Ventilator/Respirator Setting settings to be collected include: RR, TV, PEEP, Plateau Pressure; NIPPV settings (if appropriate): RR, IPAP, EPAP, FiO2; HFNC settings (if appropriate): FiO2, flow
- g. Neurological exams are to be performed every time room access is breached.
- h. For patients already on therapeutic heparin, continue heparin infusion. For patients not already on heparin or other anticoagulant, begin heparin with tenecteplase infusion starting with bolus dose of 60 Units/kg IV once, followed by 12 Units/kg/hr. For patients who were receiving enoxaparin at time of inclusion, tenecteplase infusion can be given immediately. Delay heparin to 12 hours after the most recent enoxaparin dose, beginning at an infusion rate of 18 Units/kg/hr. Do not administer a bolus dose of heparin and check PTT every 6 hours; adjust heparin to achieve target PTT of 70-90 seconds.
- i. All image collection should follow institution specific standard of care guidelines.

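### The respiratory item lists do not reliably supply FiO2 for the P/F ratio at 24 and 72 hours: NRB has flow only, low-flow oxygen has no item, and the flowchart contradicts Section 4.5.2 for ventilated patients

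*Combined protocol and SAP*

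**What the plan says.** Section 2.3 lists "P/F ratio at 24 hours and 72 hours" among the secondary outcomes. Section 1.5 describes the same outcome as "improvement in PaO₂/FiO₂", which implies that a baseline value is needed as well.

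Section 4.1.1 admits patients on "non-rebreather (NRB) mask or non-invasive positive pressure ventilation (NIPPV) for less than 96 hours", so NRB is a qualifying mode of support.

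Section 4.5.2 gives the respiratory items by device:
- Ventilator: "Ventilator settings (if appropriate): RR, TV, PI (if PCV or PSV) FiO2, PEEP, Plateau Pressure"
- NIPPV: "NIPPV settings (if appropriate): RR, IPAP, EPAP, FiO2"
- HFNC: "HFNC settings (if appropriate): FiO2, flow"
- NRB: "NRB settings (if appropriate): flow"

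Footnote f of the Appendix 1 flowchart gives a second list. It opens "Ventilator/Respirator Setting settings to be collected include: RR, TV, PEEP, Plateau Pressure" and continues with NIPPV and HFNC, both with FiO2. Ventilator FiO2 is absent, and so is NRB.

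Sections 4.5.3 and 4.5.4 repeat the respiratory status and ventilator heading without items of their own; under 4.5.4, collection runs every 6 hours to 72 hours. Blood gases are scheduled over the same period: every 6 hours for 24 hours and then daily in Section 4.5.4, every 12 hours in the flowchart. Section 6 gives no derivation of P/F and no conversion from flow to FiO2. Its only missing-data rule, carry-forward, is stated under the primary efficacy variable (Section 6.2).

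**The concern.** P/F is a quotient, and both parts must be known at the same time. The plan schedules the numerator for everyone through 72 hours but specifies the denominator only for some devices.

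Two different problems follow. For NRB patients, FiO2 has to be estimated from flow, and without a fixed rule the analyst chooses the estimate. For patients who improve to low-flow oxygen by 24 or 72 hours, no input is specified at all. If their P/F values drop out, the values lost belong to patients who did well, and the arm with more weaning loses more of its good values.

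Section 3.3 says that the trial is not powered for significance and is meant to estimate a benefit signal for a phase III trial. Section 1.5 cites improved oxygenation within 24 to 48 hours in five treated patients as part of the rationale. P/F at 24 and 72 hours bears on that observation, so a distorted estimate would matter for the trial's stated purpose even though P/F is not a primary endpoint.

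**Working it through.** The documents give no expected value, standard deviation or power for P/F, so there is no figure to reproduce. The check is a comparison of the two item lists by support mode, followed by illustrations on stated assumptions.

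**Step 1. Is the denominator specified?**

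| Support mode | Section 4.5.2 | Footnote f | P/F at 24 and 72 h |
|---|---|---|---|
| Ventilator | FiO2 listed | FiO2 omitted | Computable if 4.5.2 governs; the lists conflict |
| NIPPV | FiO2 listed | FiO2 listed | Computable |
| HFNC | FiO2 listed | FiO2 listed | Computable |
| NRB | Flow only | No line | Estimate from flow only; no rule given |
| Low-flow oxygen | No item | No item | No specified input |
| Room air | No item | No item | FiO2 is 0.21, if room-air status is recorded |

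Applying the Section 4.5.2 list after randomization is an inference from the shared heading; Section 4.5.4 has no list of its own.

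**Step 2. How many NRB patients? (assumed shares)**

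The planned total is 60 (Section 4.1). With a share *s* on NRB at a time point, 60 × *s* patients lack a recorded FiO2:
- *s* = 10%: 60 × 0.10 = 6
- *s* = 30%: 60 × 0.30 = 18
- *s* = 50%: 60 × 0.50 = 30

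**Step 3. How much does the NRB conversion matter? (assumed PaO2 and FiO2)**

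P/F = PaO2 / FiO2. With PaO2 of 70 mmHg:
- FiO2 0.6: 70 / 0.6 = 117
- FiO2 0.8: 70 / 0.8 = 87.5
- FiO2 1.0: 70 / 1.0 = 70

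The same blood gas gives 117 or 70 depending on the conversion chosen.

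**Step 4. What can loss of weaned patients do? (assumed means and shares)**

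Suppose that patients weaned to a mode with no recorded FiO2 truly average 300 and all others 150, the same in both arms. With a share *w* weaned, the arm mean is 300*w* + 150(1 − *w*).
- Tenecteplase, *w* = 0.30: 90 + 105 = 195
- Control, *w* = 0.10: 30 + 135 = 165
- True difference: 195 − 165 = 30
- Observed difference with weaned patients missing: 150 − 150 = 0

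With 20% against 10% weaned, the true difference is 180 − 165 = 15 and the observed difference is again 0. With equal shares (10% in each arm), both are 0, so the distortion of the comparison arises only when weaning differs by arm. In the 30% against 10% case, 40 × 0.70 = 28 and 20 × 0.90 = 18 patients would remain in the analysis. Deaths are ignored here.

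**The case against.** The strongest reply is that little is truly uncollectable, and much of it stands.

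- A reader might infer that P/F cannot be computed for ventilated patients. The documents do not support that: Section 4.5.2 lists ventilator FiO2. The shorter footnote f contradicts it, and the two must be reconciled, but this is not proof of absent data.
- For NRB, the body text records the device and its flow, so a fixed conversion would yield an estimate. What is missing is the rule, and the NRB line in footnote f.
- A reader might infer that every patient weaned by 72 hours will be missing. That is not shown. The item list sits under Screening, where every eligible patient is on one of the four listed modes, so it needed no further lines there. Section 4.5.4 asks for respiratory status without limiting it to those items, and room-air FiO2 is known once the status is recorded. The case report forms mentioned in Section 7.5 are not among the documents and may hold more. The accurate description is that the input is not specified. The ordinal scale in the flowchart does not settle the matter, because its categories are not defined.
- A reader might treat all of this as outcome-dependent missingness. That fits low-flow oxygen. The NRB gap follows the device and already exists at baseline, before any treatment effect.
- A reader might rank P/F as the main early physiological outcome. Section 2.3 does not rank it; vasopressor requirement is measured at the same two times, and no primary endpoint uses P/F.

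After these limits, three defects remain: the conflict over ventilator FiO2, the absence of any flow-to-FiO2 rule, and the absence of an item for low-flow oxygen or room air after randomization.

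**Conclusion.** The point holds in a limited form. Followed as written, the item lists leave FiO2 contradictory for ventilated patients, estimable but without a rule for NRB patients, and unspecified for patients weaned to low-flow oxygen. The last gap depends on a favourable result and could bias the P/F comparison towards no effect if weaning is more common on tenecteplase.

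The size cannot be taken from the documents, which state neither the NRB share nor the weaning rate. The 6 to 30 patients, the P/F range of 70 to 117 and the lost difference of 15 to 30 rest on the assumed shares, blood gas and means shown above. They illustrate the mechanism and are not forecasts. The low-flow conclusion also assumes that the case report forms follow the printed lists.

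This is a minor, easily repaired weakness in a secondary outcome. It does not touch the primary efficacy or primary safety endpoint.

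**What to change.** 1. At baseline and at each blood gas through 72 hours, record the device and either FiO2 or flow for every support mode, including NRB, low-flow oxygen and room air (0.21).
2. Fix one flow-to-FiO2 conversion in the statistical section before unblinding.
3. Align footnote f with Section 4.5.2 by adding ventilator FiO2 and an NRB line.
4. Compare P/F at 24 and 72 hours adjusted for baseline P/F.

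The cost is one or two eCRF fields, a corrected footnote and a short addition to Section 6, with no added patient procedure. The limitation is that FiO2 for NRB and low-flow oxygen remains an estimate; a fixed rule makes it consistent across arms but does not make it a measurement. An FiO2 or flow not written down at the bedside may not be recoverable later, so the fields should be in place before patients are enrolled. Giving deaths the worst rank is a separate, optional analysis choice that this repair does not require.

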4.5.3 Pre-Randomization

All study assessments during Pre-Randomization must be collected or confirmed within 2 hours of study drug administration.

- Neurological Exam
- Vitals
- Laboratory Samples

CBC: Platelet, WBC, Hb, Hct

BMP: Na, K, Cl, HCO3, BUN, Cr

Glucose (finger stick or lab)

LFT: ALT, AST, Bili, Alk Phos, LDH, Total Protein, Albumin, D-dimer, fibrinogen, CRP, ferritin, troponin-I, BNP

Coagulation: INR, aPTT, PT, anti-Xa

Thromboelastograms (when available according to standard practice)

- Respiratory Status / Ventilator Settings
- Ordinal Scale Assessment
- Concomitant medication review (excluding "prn" or "as needed" medications)

4.5.4 Post-Randomization

Post Randomization assessments will be collected every 6 hours up to 72 hours after study drug administration.

- Randomization and Study Drug Administration
- Neurological Exam

Tenecteplase-Icahn School of Medicine at Mount Sinai
Protocol ML42492

The subject will be evaluated every 15 minutes for the first hour following study drug administration. Evaluation will then occur every 30 minutes for 4 hours, then every hour for 12 hours. The neurological exam will be documented by a GCS score and NIHSS.

- Vitals

Vital signs should be measured every 15 minutes after study drug administration for one hour, then every hour for 4 hours, then every 6 hours.

- Laboratory Samples (q6 hours for 24 hrs and then daily for subsequent 48 hours)

Coagulation: INR, aPTT, PT, anti-Xa

Arterial Blood Gas: pH, pCO₂, pO₂, SaO₂, Lactate

- Respiratory Status / Ventilator Settings

- Doses of all vasopressors every 6 hours for first 72 hours then daily

- Heparin Dosing

If subject was not previously on heparin, please begin infusion as specified in protocol. Begin heparin with tenecteplase infusion starting with bolus dose of 60 Units/kg IV once, followed by 12 Units/kg/hr. Heparin should be adjusted to achieve target PTT of 70-90 seconds.

- Concomitant medication review (excluding “prn” or “as needed” medications)

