Tenecteplase has also been assessed for use in treating pulmonary embolism (PE). In general, thrombolysis for PE has been shown to have minimal evidence for clinical benefit compared with heparin, except in those with the highest risks of recurrence or death.³² In clinical trials, thrombolysis with alteplase has been associated with improvements in hemodynamic parameters (including pulmonary resistance and cardiac index) but have indeterminate effects on overall clinical outcomes given a paucity of data.³³ In one randomized, placebo-controlled trial of tenecteplase (at a dose of 0.5 mg/kg) plus heparin versus heparin alone, intermediate-risk patients with PE treated with TNK had lower risk of hemodynamic decompensation or death.³⁴ Symptomatic intracranial hemorrhage was more frequent in the TNK group, though occurred predominantly in patients older than 75 years old. Patients with submassive PE have also been found to have increased odds of good outcome after treatment with tenecteplase, compared with placebo, according to a randomized trial published in 2014.³⁵

Based on this evidence, dosing guidelines for this trial will be as follows:

Patients will be monitored in the ICU immediately post-treatment and until 24 hours have passed and they are considered stable to downgrade to lower level of care.

- A. For patients already on therapeutic heparin, continue heparin infusion
- B. For patients not already on heparin or other anticoagulant, begin heparin with tenecteplase infusion starting with bolus dose of 60 Units/kg IV once (maximum dose of 5000 Units), followed by 12 Units/kg/hr (patients will only receive one dose of tenecteplase in total)
- C. For patients who were receiving enoxaparin at time of inclusion, tenecteplase infusion can be given immediately. Delay heparin to 12 hours after the most recent enoxaparin dose, beginning at an infusion rate of 12 Units/kg/hr. Do not administer a bolus dose of heparin.

-Check PTT every 6 hours; adjust heparin to achieve target PTT between 2 and 2.5 times ULN

Tenecteplase–Icahn School of Medicine at Mount Sinai
Protocol ML42492

12

Patients will continue with the unfractionated heparin infusion for 24 hours from the beginning of the study. After 24 hours, they may be transitioned to low molecular weight heparin according to institutional standard of care.

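### Section 4.5.4 orders a heparin bolus for any subject not previously on heparin, contradicting the no-bolus, 12-hour-delay rule for enoxaparin patients in 3.3.1 and Appendix 1 note h

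*Combined protocol and SAP*

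**What the plan says.** Heparin instructions appear in three places.

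- **Section 3.3.1** gives three pathways. Under A, patients already on therapeutic heparin continue it. Pathway B opens "For patients not already on heparin or other anticoagulant, begin heparin with tenecteplase infusion" and gives a 60 Units/kg bolus (maximum 5000 Units), then 12 Units/kg/hr. Pathway C reads "For patients who were receiving enoxaparin at time of inclusion, tenecteplase infusion can be given immediately"; it then instructs "Delay heparin to 12 hours after the most recent enoxaparin dose", and it rules out a bolus and sets the starting rate at 12 Units/kg/hr.
- **Appendix 1, note h** repeats the same three branches, including the wider condition on the bolus and, for enoxaparin patients, the ban on a bolus and the 12-hour delay.
- **Section 4.5.4**, the procedures around and after study drug administration, has one branch. It says "If subject was not previously on heparin, please begin infusion as specified in protocol" and continues "Begin heparin with tenecteplase infusion starting with bolus dose of 60 Units/kg IV once, followed by 12 Units/kg/hr". It mentions neither other anticoagulants nor enoxaparin.

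**The concern.** Section 4.5.4 copies the dose from pathway B but widens the group that receives it. A patient on enoxaparin and not on unfractionated heparin fails pathway B's condition in 3.3.1 but meets the condition in 4.5.4. The two sections then give opposite instructions for the same patient at the same moment.

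Such patients can be enrolled. The exclusions in 4.1.2 cover the newer oral anticoagulants within 24 hours and set INR limits; they do not name enoxaparin, and pathway C exists because such patients are expected.

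What is at stake is bleeding. Section 4.4.1 warns that anticoagulants given before, during or after tenecteplase may raise bleeding risk. Intracranial or major bleeding within 72 hours is the primary safety outcome in 2.3, and the safety trigger in 4.2 is a difference of more than two patients between arms in symptomatic intracranial hemorrhage or major bleeding. A bleed that followed a bolus the protocol meant to forbid would harm a patient and would also count in a small safety comparison.

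**Working it through.** The plan gives no figure to reproduce. The check is a comparison of texts, followed by arithmetic on how far the two orders differ.

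**Orders by patient type**

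| Patient at inclusion | 3.3.1 and note h | 4.5.4 read literally |
|---|---|---|
| On therapeutic heparin | Continue | No new order |
| On no anticoagulant | Bolus 60 Units/kg, then 12 Units/kg/hr | Same |
| On enoxaparin | No bolus; heparin starts 12 h after last dose | Bolus 60 Units/kg with study drug, then 12 Units/kg/hr at once |
| On another anticoagulant, still eligible | Excluded from the bolus branch; no other branch named | Bolus 60 Units/kg, then 12 Units/kg/hr |

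The third row is a direct contradiction. In the fourth, 4.5.4 supplies an order where 3.3.1 withholds one.

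**Inputs for the dose difference**

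- Bolus 60 Units/kg and rate 12 Units/kg/hr: section 4.5.4.
- No bolus, start at 12 hours after the last enoxaparin dose, rate 12 Units/kg/hr: section 3.3.1 C.
- Window of 6 hours, to the first PTT check: 3.3.1 requires a check every 6 hours, and the laboratory line of 4.5.4 begins "Laboratory Samples (q6 hours for 24 hrs and then daily for subsequent 48 hours".
- *t*, hours from the last enoxaparin dose to study drug: not in the documents, so shown as a range.
- Body weight: assumed 60 kg and 80 kg. Both are below 5000 / 60 = 83.3 kg, the weight at which the 3.3.1 bolus cap begins to bind, so the cap does not affect the examples.

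**Formulas (Units/kg over the first 6 hours)**

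- Section 4.5.4: 60 + 12 × 6 = 132.
- Pathway C: 12 × [6 − min(6, max(0, 12 − *t*))].
- Excess: 60 + 12 × min(6, max(0, 12 − *t*)).

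| *t* | 4.5.4 | Pathway C | Excess | 60 kg | 80 kg |
|---|---|---|---|---|---|
| 12 h or more | 132 | 12 × 6 = 72 | 60 | 3,600 Units | 4,800 Units |
| 9 h | 132 | 12 × 3 = 36 | 96 | 5,760 Units | 7,680 Units |
| 6 h or less | 132 | 0 | 132 | 7,920 Units | 10,560 Units |

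The excess is also the amount 4.5.4 gives before pathway C would have started any heparin: the bolus alone at 12 hours or more, and the bolus plus 3 or 6 hours of infusion in the other rows.

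Note h gives 18 rather than 12 Units/kg/hr for these patients, which is a separate discrepancy. At that rate the six-hour excess would be 132 − 108 = 24, 132 − 54 = 78 and 132 − 0 = 132 Units/kg. The amount given before heparin is permitted stays at 60, 96 and 132.

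**The case against.** The strongest reply is that the protocol already resolves this. The sentence in 4.5.4 refers the reader back to the protocol's specification; sections 4.3, 4.3.2 and 4.3.2.1 send dosing questions to 3.3.1; and section 4.5 opens by pointing to the Appendix 1 schedule, whose heparin row carries note h. On this view 4.5.4 is an incomplete summary inside an assessment list. That establishes which rule was intended. It does not cancel the order that follows, which states dose, route, timing and rate and gives no sign that an exception exists.

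A second reply is that enoxaparin is itself a heparin. Section 3.3.1 uses the wider term when it says that after 24 hours "they may be transitioned to low molecular weight heparin according to institutional standard of care". A site reading it this way would give no bolus under 4.5.4. But 3.3.1 and note h treat heparin and enoxaparin as separate pathways, and even on this reading 4.5.4 says nothing about the 12-hour delay.

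Three narrower points stand:

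- The eligibility criteria remove most patients on other anticoagulants, so the practical consequence is nearly all in the enoxaparin group. Some could remain, such as a patient recently on oral anticoagulant therapy with an INR of 1.7 or below.
- The finding reported in 3.3.1, that lower heparin infusion rates reduced hemorrhage in an earlier tenecteplase trial, does not bear directly on an added bolus or an earlier start. The conclusion does not rely on it.
- No passage estimates the bleeding risk of a heparin bolus on top of enoxaparin, so the size can be given only as a dose.

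**Conclusion.** The concern holds. Section 4.5.4 is wrong as written: for a patient on enoxaparin it orders a bolus that 3.3.1 and note h forbid and, within 12 hours of the last enoxaparin dose, an infusion that they delay. On the 3.3.1 rate the excess to the first PTT check runs from 60 to 132 Units/kg, or 3,600 to 7,920 Units at 60 kg and 4,800 to 10,560 Units at 80 kg. The weights and the enoxaparin timings are assumptions. The number of patients who would arrive on enoxaparin is unknown, so no count of affected patients or of extra bleeds is claimed.

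The governing section is correct, so the design itself is sound. The change should still be made, because the conflicting order bears on the primary safety outcome and is simple to remove. Confidence is high, since the point rests on the text.

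**What to change.** In section 4.5.4, delete the two sentences quoted above and put in their place: *Give heparin according to the patient's pathway (A, B or C) in Section 3.3.1.*

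This is one replaced passage in an amendment. Eligibility, sample size and analysis are unaffected. The cost is that staff using 4.5.4 as a checklist must turn to 3.3.1 for the dose.

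The edit does not settle everything in the heparin text. Section 3.3.1 still has no pathway for an eligible patient on an anticoagulant other than therapeutic heparin or enoxaparin. The differences in PTT target (2 to 2.5 times ULN in 3.3.1, 70-90 seconds in 4.5.4 and note h) and in the enoxaparin infusion rate (12 against 18 Units/kg/hr) also remain, as does the missing bolus cap in note h. These are separate points that the same amendment could address.
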